## 9.1.4. Study Population

The study population will include CMS Medicare FFS beneficiaries aged 65 years of age or older and PharMetrics Plus enrollees aged 60-64 years who receive one dose of ABRYSVO vaccine administration during the surveillance period and meet all other eligibility criteria (Section 9.2.1.1 and 9.2.1.2).

The SCRI analysis will be conducted in the study populations identified in both the 2023/2024 and 2024/2025 RSV seasons; the RCA analysis will be launched in the 2024/2025 RSV season, with cumulative data from the 2023/2024 RSV season (Figure 7).

The descriptive analysis for commercially insured adults aged 60-64 years will be conducted in the study populations identified in both the 2023/2024 and 2024/2025 RSV seasons (Figure 7).

Figure 7. The overall study design flowchart and population selection

Abbreviations: CMS, Centers for Medicare and Medicaid Services; RCA, rapid cycle analysis; RSV, respiratory syncytial virus; SCRI, self-controlled risk interval.

### 9.2. Setting

The source population is U.S. Medicare beneficiaries available in the CMS Medicare FFS administrative database. This database includes Medicare Parts A, B, and D data, covering inpatient and outpatient encounters and drug/vaccine prescriptions. The source population also includes individuals aged 60-64 years in the PharMetrics Plus database, which provides comprehensive claims data on healthcare utilization, including inpatient and outpatient encounters, and drug/vaccine prescriptions.

Individuals aged 65 years of age or older in the CMS Medicare data and individuals aged 60-64 years in PharMetrics Plus database who receive ABRYSVO vaccine (i.e., exposure) who meet the eligibility criteria described in Sections 9.2.1.1 and 9.2.1.2 will be included in the study.

The ABRYSVO vaccine record will be identified using CPT (Current Procedural Terminology), HCPCS (Healthcare Common Procedure Coding System), and NDC (National Drug Code) codes. The details of the exposure and other inclusion and exclusion criteria are defined in Section 9.3.

### 9.2.1. Inclusion and Exclusion Criteria

## 9.2.1.1. Inclusion Criteria

Individuals in CMS Medicare databases must meet all of the following inclusion criteria to be eligible for inclusion in the study:

- 1. Receiving one dose of ABRYSVO vaccine administration (identified by specific CPT, HCPCS, or NDC codes) during the respective indexing period:
  - a. RCA analysis:
    - i. 2023/2024 and 2024/2025 RSV seasons RCA analysis: 31 May 2023 to 10 January 2025 (Section 9.3.1);
  - b. SCRI analysis:
    - i. 2023/2024 RSV season SCRI analysis: 31 May 2023 to 29 February 2024:
    - ii. 2024/2025 RSV season SCRI analysis: 31 May 2024 to 28 February 2025:
    - iii. Combined two seasons SCRI analysis: 31 May 2023 to 28 February 2025;
- 2. At least 65 years of age on the index date (Section 9.3.3);
- 3. Medicare beneficiaries who aged into Medicare (Section 9.3.3);
  - Note: Beneficiaries who qualify due to disability differ from beneficiaries who
    qualify due to age in several ways, including their demographic,
    socioeconomic, and health status profiles. To reduce potential confounding
    from this specific frail Medicare population that could have a different
    association between vaccination and GBS, they are not included in the study
    population.
- 4. At least 12 months of continuous enrollment in Medicare Parts A and B prior to the index date (i.e., the baseline period) (Section 9.3.3);
- 5. A minimum period of continuous enrollment in Medicare Part D (e.g., 3 months) prior to the index date;
  - Note: this requirement is to balance subject attrition and adequate capture of recent prescriptions prior to vaccination. The minimum period of continuous enrollment in Medicare Part D will be specified in the SAP after feasibility assessment.

6. No record of an RSV vaccine from a manufacturer other than Pfizer during the baseline and the follow-up period (Section 9.3.1).

Individuals in the PharMetrics Plus database must meet all of the following inclusion criteria to be eligible for inclusion in the study:

- 1. Receiving one dose of ABRYSVO vaccine administration (identified by specific CPT, HCPCS, or NDC codes) during the respective indexing period (Section 9.3.1):
  - a. Indexing period for descriptive analysis:
    - i. 2023/2024 RSV season analysis: 31 May 2023 to 29 February 2024;
    - ii. 2024/2025 RSV season analysis: 31 May 2024 to 28 February 2025;
    - iii. Combined two seasons analysis: 31 May 2023 to 28 February 2025;
- 2. Aged 60-64 years on the index date (Section 9.3.3);
- 3. At least 12 months of continuous enrollment with medical and pharmacy benefits in PharMetrics Plus database prior to the index date (i.e., the baseline period) (Section 9.3.3);
- 4. No record of an RSV vaccine from a manufacturer other than Pfizer during the baseline and the follow-up period (Section 9.3.1).

## 9.2.1.2. Exclusion Criteria

Individuals in CMS Medicare databases and the PharMetrics Plus database meeting any of the following criteria will not be included in the study:

- 1. Individuals without sex information (Section 9.3.3);
- 2. Individuals with a GBS diagnosis on a claim in any position and any setting during the baseline period or on the index date (Section 9.3.2).

## 9.3. Variables

Exposures, outcomes, and covariates will be identified within relevant care settings in the claims data. The care setting of the IP and OP/PB settings used in this study are defined in Section 9.4.

## 9.3.1. Exposure

The exposure of interest is ABRYSVO vaccination, defined as an individual's first administration of the ABRYSVO vaccine during the indexing period (Section 9.1.1), as identified by a CPT code, HCPCS code or NDC during the indexing period. (21)

The study spans two RSV seasons, 2023/2024 and 2024/2025, and multiple vaccinations are not anticipated as ABRYSVO is currently not approved for re-vaccination and evidence

suggests that ABRYSVO provides protection for at least two RSV seasons that overlap with the study period. To deduplicate exposure occurrences, multiple vaccine records containing the same ABRYSVO vaccine product for a unique patient ID, occurring on the same day or within three days will be deduplicated. If the multiple vaccine records are more than three days apart for a unique patient ID, it will be flagged as off-label use and reported separately. The date of the first occurrence of the ABRYSVO vaccination will be defined as the index date.

The example code lists for ABRYSVO vaccine and RSV vaccines from a manufacturer other than Pfizer is listed in LIST OF CODES FOR RSV VACCINES. The list of RSV vaccine codes in the example code lists will be reviewed and updated periodically during the entire study period.

#### 9.3.2. Outcomes

The outcome of interest is GBS diagnosis, which will be identified from IP and OP claims using ICD-10-CM code G 61.0.

An incident GBS case will be defined as the first occurrence of a primary discharge diagnosis of GBS in the IP setting post-vaccination. The date of the case's onset will be defined as the date of hospitalization unless there is a claim with a GBS diagnosis in another medical setting (e.g., OP) in the prior 7 days. In that case, the earlier claim, irrespective of healthcare setting, will represent the date of onset. This claims-based algorithm in Medicare data has a PPV of 71.2% – 78.6% when validated against medical records using the Brighton criteria and has been used to reliably identify GBS cases among Medicare beneficiaries.(9, 22, 23) In a recent FDA analysis evaluating GBS risk following RSV vaccination in the Medicare data, the algorithm for GBS had a PPV of 62.3% in the post-vaccination risk interval of 1-42 days and a PPV of 81.8% in the post-vaccination control interval of 43-90 days, based on chart review.(24)

The risk window of 42 days post-vaccination is generally recommended by the Brighton Collaboration GBS case definition. (19) Within the ABRYSVO clinical and surveillance studies, over 90% of GBS events have been found to occur within 21 days of vaccination.(13) In this study, for the RCA, the primary risk interval is defined as 1—21 days post-vaccination to prioritize timely analysis; a secondary risk interval of 1—42 days post-vaccination will also be analyzed. For the SCRI, the primary post-vaccination risk interval is defined as 1—21 days post-vaccination and the secondary post-vaccination risk interval is defined as 1—42 days post-vaccination. The control interval for the SCRI analysis is defined as 43—84 days post-vaccination. For the SCRI analysis, GBS diagnosis will be identified during the risk and the control intervals to compare the risk of GBS occurrence within the two intervals.

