#### 9. RESEARCH METHODS

## 9.1. Study Design

This will be a non-interventional cohort study among older adults enrolled in CMS Medicare databases and PharMetrics Plus database (Section 9.4). The surveillance period for RSV vaccinations (i.e., the indexing period) will span 2 RSV seasons (i.e., 2023/2024 and 2024/2025 seasons), beginning on ABRYSVO's approval on 31 May 2023. Two RSV seasons are included to increase sample size and rapidly assess a modest to high risk (3- to 5-fold) of GBS after ABRYSVO vaccination while a separate, long-term PMR PASS (protocol # C3671031) spanning 4.5 RSV seasons or more is being conducted to detect any small risk of GBS (e.g., 2-fold) following ABRYSVO vaccination using the fully adjudicated claims in CMS Medicare. There will be descriptive monitoring of GBS incidence following ABRYSVO vaccination among adults aged 60-64 years of age.

The baseline period for an individual will be defined as 365 days prior to the date of the ABRYSVO administration (i.e., the index date), to assess the individual's demographic and clinical characteristics, and to rule out prevalent GBS cases. Two complementary approaches will be used to address the study objectives and evaluate the risk of GBS among individuals who receive ABRYSVO: RCA and SCRI. A patient-level case-centered analysis will also be conducted to better understand the severity and risk factors associated with all GBS cases identified in the analytic populations from two databases: CMS Medicare administrative databases and PharMetrics Plus database. The CMS Medicare database covers individuals aged 65 and older, while PharMetrics Plus data will cover individuals aged 60-64 years. Together, these two data sources will provide age representation for the currently approved indication for ABRYSVO for older adults. Given the more limited age range for commercially insured adults 60-64 years, analyses for this age group will be primarily descriptive based on available sample size.

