## 9.1.2.1. The Study Periods of SCRI Methodology

[figure not shown]
The SCRI analysis spans the 2023/2024 and 2024/2025 RSV seasons, and the follow-up period consists of the pre-specified post-vaccination risk and control intervals. The key study periods of the SCRI analysis are described below:

- Study Periods:
  - o **2023/2024 Study Period:** 31 May 2022 23 May 2024
    - **Indexing period:** 31 May 2023 29 February 2024

- o **2024/2025 Study Period:** 31 May 2023 23 May 2025
  - Indexing period: 31 May 2024 28 February 2025
- o Combined two season study period: 31 May 2022 23 May 2025
  - **Indexing period:** 31 May 2023 28 February 2025
- Note: As detailed in Section 9.1.2, the indexing period will end in February as >90% of RSV vaccinations are anticipated to be administered by that time, as a trade-off to balance timely analyses and more complete data capture.
- Index Date: The date of ABRYSVO administration
- **Baseline period:** 365 days prior to the index date
- Follow-up period:
  - Post-vaccination risk period: 1-21 and 1-42 days after the index date as the primary and secondary risk interval, respectively. Days 22-42 after the primary 1-21 days risk interval will be considered a washout period and will not be included in the analyses to avoid any carryover effects.
  - o **Post-vaccination control period:** 43-84 days after the index date

Figure 3 shows the study design and key study periods of the SCRI analysis.

[figure not shown]
Figure 3. Study design of the self-controlled risk interval analysis

Abbreviations: Dx, diagnosis; GBS, Guillain-Barre syndrome; RSV, Respiratory Syncytial Virus.

Figure 4 shows the study period of SCRI analysis in relation to the RSV seasons.

Figure 4. The study period of self-controlled risk interval analysis during 2023/2024 and 2024/2025 RSV seasons

Abbreviations: GBS, Guillain-Barre Syndrome; RSV, respiratory syncytial virus; SCRI, self-controlled risk interval.

Note: The data maturation period allows for claims in the CMS Medicare FFS administrative database to be completed in the system. Historically, approximately 90% of Medicare IP and OP claims were submitted to the CMS within 2 months after service date. (14, 15)

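### In the SCRI, a GBS code on days 1-42, more than 7 days before a primary-GBS admission on days 43-84, does not stop that admission counting as a control case; this biases the IRR downward by an unknown amount

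*Protocol*

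**What the plan says.** Section 9.2.1.2 removes "Individuals with a GBS diagnosis on a claim in any position and any setting during the baseline period or on the index date". Section 9.1 gives the purpose of the 365-day baseline, in part, as "to rule out prevalent GBS cases".

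After vaccination a different rule applies. Section 9.3.2 states: "An incident GBS case will be defined as the first occurrence of a primary discharge diagnosis of GBS in the IP setting post-vaccination". Onset is the admission date "unless there is a claim with a GBS diagnosis in another medical setting (e.g., OP) in the prior 7 days"; then "In that case, the earlier claim, irrespective of healthcare setting, will represent the date of onset".

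The same section sets the windows: "the primary post-vaccination risk interval is defined as 1—21 days post-vaccination", and "The control interval for the SCRI analysis is defined as 43—84 days post-vaccination". Section 9.1.2.1 says that days 22-42, in the primary analysis, "will be considered a washout period and will not be included in the analyses to avoid any carryover effects". No screen for GBS codes is attached to those days.

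**The concern.** Before vaccination, any G61.0 code removes the person. After vaccination, only an earlier inpatient primary diagnosis makes a later one non-incident. An outpatient or professional code more than 7 days before admission neither excludes nor re-dates the case. An inpatient secondary code may also escape at any distance, since the look-back refers to another medical setting.

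The two windows are affected unequally. A late-admitted case that would fall in days 1-21 has mostly been coded before vaccination, so it is excluded. A late-admitted case that falls in days 43-84 may have been coded first on days 1-42, and it is kept as a new control onset. If that first code lay on days 1-21, the risk window also loses a case.

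The SCRI is the analysis that is to evaluate any RCA signal (Sections 9.7.3 and 9.9.2). An error toward no risk is the unfavourable direction there. None of the analyses in Sections 9.7.6 and 9.7.7 (seasonality, PPV, complete follow-up, prior infection, secondary RCA interval, case-centered description) screens or re-dates on an earlier GBS code.

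**Working it through.** **Inputs from the protocol.** About 1 million eligible per season and 2 million pooled; background rate 4.6 per 100,000 person-years (Section 9.5); windows and look-back as above. **Assumed:** the share f of cases whose first GBS code precedes the primary admission by more than 7 days. The protocol does not give it, so 2%, 5% and 10% are shown.

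**Plan's own figure.** Table 1 reproduces. For IRR 5.0, 15 events give 15/6 = 2.5, rounded up to 3, in the control interval. The 21-day rate is 4.6e-5 × 21/365.25 = 2.64e-6. With 2.6e-6, N = 3/2.6e-6 = 1,153,846, as printed. This point challenges nothing in that table.

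**Unscreened days.** For onset on day d, the post-index days before the look-back number max(0, d − 8). Their average is 91/21 = 4.3 over days 1-21 and 55.5 over days 43-84.

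**Expected counts, primary analysis, one season.** Control: 1,000,000 × 4.6e-5 × 42/365.25 = 5.29. Risk: 2.64 × IRR, which is 7.93 at IRR 3 and 13.22 at IRR 5. Because the control window is twice as long, IRR = 2 × risk/control.

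| Change | True IRR 5 | True IRR 3 |
|---|---|---|
| One season, one case added to control | 2 × 13.22/6.29 = 4.2 | 2 × 7.93/6.29 = 2.5 |
| One season, one case moved from risk to control | 2 × 12.22/6.29 = 3.9 | 2 × 6.93/6.29 = 2.2 |
| Pooled, one case added to control | 2 × 26.45/11.58 = 4.6 | 2 × 15.87/11.58 = 2.7 |
| Pooled, one case moved | 2 × 25.45/11.58 = 4.4 | 2 × 14.87/11.58 = 2.6 |

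**Day-by-day model.** Let true onset be the first code, and let a share f of cases be admitted g days later, with g uniform on 8-42 (35 values). Anyone first coded on or before day 0 is excluded. Work in units of one day's background cases.

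- Delayed cases admitted on days 1-21 with a first code on day 1 or later: (13 + 12 + … + 1)/35 = 91/35 = 2.6 onset days instead of 21, each at rate IRR.
- Delayed cases admitted on days 43-84: 42 onset days, of which (1 + 2 + … + 21)/35 = 231/35 = 6.6 lie in days 1-21 and carry rate IRR.
- Observed IRR = 2 × IRR × (21 − 18.4f) / (42 + 6.6f(IRR − 1)).

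Example, IRR 5 and f = 5%: 10 × 20.08/43.32 = 4.64.

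| f | True IRR 1 | True IRR 3 | True IRR 5 |
|---|---|---|---|
| 2% | 0.98 | 2.93 | 4.85 |
| 5% | 0.96 | 2.82 | 4.64 |
| 10% | 0.91 | 2.65 | 4.29 |

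At a true IRR of 1 the control count is unchanged and the deficit is all in the risk window. Above 1 the control window also gains. The 42-day analysis is biased the same way: IRR × (42 − 25f)/(42 + 25f(IRR − 1)) turns 3 into 2.90, 2.75 or 2.52.

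**Do the repairs work?** Dropping all cases with a gap over 7 days leaves 21(1 − f) × IRR against 42(1 − f), which is the true IRR. Dating onset at the first code also restores it, provided that admissions after day 84 are captured. If admissions stop at day 84, delayed control cases yield (34 + 33 + … + 0)/35 = 17 onset days instead of 42. IRR 5 at f = 5% then becomes 5 × 42/(0.95 × 42 + 0.05 × 17) = 5.15, a small bias the other way.

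**The case against.** Four objections carry weight.

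- **The gap is narrower than it may look.** A reader might infer that any outpatient code on days 1-42 leaves a later admission in the control window. It does not. A code on day 40 with admission on day 45 is dated to day 40, outside the control window. An earlier inpatient primary diagnosis also blocks a later one.
- **The washout helps.** A reader might infer that this carry-over defeats it. In fact a case coded on days 1-21 needs a gap of at least 22 days to reach day 43. Under the 8-42-day model only 6.6/21 = 31% of delayed risk-window cases do so, and Section 7 describes GBS as an acute disease. A first code on days 22-42 adds to control but removes no primary risk case.
- **Larger figures need a stronger assumption.** If f meant the share of risk and washout cases that actually land in days 43-84, IRR = 2R(1 − f)/(C + f(R + W)), with R = 13.22, W = 2.64 and C = 5.29. That gives 4.6, 4.1 or 3.5 at 2%, 5% or 10%. Landing 10% of risk cases in control would need about a third of them (10/31) to be delayed. The formula also lets control gain cases but never lose them.
- **The definition is the validated algorithm.** Its PPVs feed the bias analysis in Section 9.7.6.2, so replacing it has a price. Section 9.7.6 also leaves room for further sensitivity analyses in the SAP.

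These limit the size of the problem and argue against replacing the primary definition. They do not remove the asymmetry: Section 9.3.2 itself fixes the case and onset rules, and no analysis described in the protocol tests them.

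**Conclusion.** The point holds as an asymmetry in the outcome rule, with a bias toward no risk in the SCRI. It does not support a claim that the bias is large, or that any such case has occurred; the protocol contains no data on either. At an assumed share of 2-5% with gaps of 8-42 days, the primary IRR falls by about 2-7%, which is small beside the sampling error on roughly five control cases. The shifts to 3.9 and 2.2 are the single-season worst case for one person; pooled, one moved case gives 4.4 and 2.6. All these results assume that the first code marks true onset. If some early codes are rule-outs, the bias is smaller.

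**What to change.** Keep the Section 9.3.2 definition as primary, for comparability and for the PPV adjustment. Prespecify, for the seasonal and pooled SCRI, one analysis that treats both windows alike:

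- **Clean period:** count a case only if no G61.0 claim, in any setting or position, falls from day 1 to 8 days before the admission; or
- **First-code dating:** for each qualifying inpatient case, set onset at the first post-index G61.0 claim and assign it to the risk, washout or control window.

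The second option needs admissions after day 84. With gaps up to 42 days, the last vaccinee (28 February 2025) would be followed for 126 days, to 4 July 2025. That is past the stated SCRI study end of 23 May 2025 but before the end of data collection on 15 September 2025. The clean period needs no such extension.

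State also whether the 7-day look-back includes inpatient secondary codes. Report the resulting IRR beside the primary one. Counts of affected cases by window fall under the suppression of values below 11 (Section 9.6), so the comparison of IRRs may be all that can be shown.

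The cost is some wording and one more filter on claims data. Some true cases may be dropped or misdated because of early rule-out codes, and the published PPVs apply less directly to the modified definition.

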#### 9.3.3. Patient Characteristics

Patient characteristics, including demographics, clinical characteristics, medications/vaccinations, and healthcare resource utilization will be captured during the baseline period and/or follow-up period, as applicable. Variables that will be assessed may

include, but are not limited to, those listed below. The final list of covariates and codes to identify those covariates will be defined in the SAP based on feasibility and availability.

## **Demographics:**

- Age
- Sex
- Race/ethnicity
- Geographic region in the U.S.

### **ABRYSVO** vaccination characteristics:

- Month and year of vaccination
- Care setting of vaccination

### **Clinical characteristics:**

- History of anaphylaxis
- Previous anaphylaxis of vaccine component
- Hospitalizations in the baseline period and during the follow-up period
- Admission into nursing home/Skilled Nursing Facility (SNF) in the baseline period and during the follow-up period
- Infections in the baseline period and during the follow-up period
  - O Upper or lower respiratory tract infections (including diphtheria, whooping cough, streptococcal sore throat and scarlet fever, varicella with pneumonia, RSV, COVID-19, acute sinusitis, acute tonsilitis, acute bronchitis, influenza, etc.)
  - o Gastrointestinal infections (including cholera, typhoid and paratyphoid fevers, shigellosis, amebic nondysenteric colitis, etc.)
  - Unspecified viral infection
  - o Diarrhea
  - o Fever
  - Campylobacter enteritis
  - o Cytomegalovirus (CMV)
  - o Epstein-Barr Virus (EBV)
  - Hepatitis E Virus (HEV)
  - Zika virus
- Frailty index
- Charlson Comorbidity Index (CCI)
- Smoking status
- Body Mass Index (BMI)
- Immunocompromised status
- Selected comorbidities
  - o Asthma
  - Blood disorders
  - o Chronic lung disease

### PFIZER CONFIDENTIAL

- Diabetes
- Heart disease
- Kidney disease
- o Liver disorders
- o Neurological conditions
- o Malignant neoplasms
- Surgery (i.e., anesthesia or conscious sedation) in the baseline period and during the follow-up period
- Trauma in the baseline period and during the follow-up period
- Prior bone marrow transplant
- Immunizations on the index date, in the baseline period, in close proximity (e.g., within 30 days) to ABRYSVO exposure, and during the follow-up period
  - Seasonal influenza vaccine
  - o COVID-19
  - o RSV (other than Abrysvo)
  - o Tetanus and Diphtheria (Td) and Tetanus, Diphtheria, Pertussis (Tdap)
  - o Chickenpox (varicella)
  - o Shingles (herpes zoster recombinant and/or live)
  - Human Papillomavirus (HPV)
  - o Pneumococcal conjugate
  - o Pneumococcal polysaccharide
  - o Hepatitis A
  - o Hepatitis B
  - Meningococcal ACWY Vaccine (MenACWY) and Meningococcal B Vaccine (MenB)
  - o Haemophilus influenzae type b
  - o Combined
- Medication use in the baseline period and during the follow-up period including, but not limited to:
  - o TNF-alpha antagonists
  - Immune checkpoint inhibitors
  - o Immunosuppressant therapies
  - Isotretinoin

